3.2. Randomization

Randomization will be stratified by site. Stratified, block randomization will ensure that an approximately equal number of patients are randomized to each treatment group by site. The exact block size will be randomly permuted (e.g., block size of 4 with probability 0.7 and 6 with probability 0.3) with block sizes and their probabilities known only to the biostatistician.

Once an eye is in the study enrolled (only one eye can be enrolled from each patient), the study coordinator will assign the study participant's eye an ID (alpha-numeric code) and organize the procedure in the operating room within 48 hours of enrollment. Once the study participant has been assigned a study participant ID and randomized to treatment arm, they will be included in the intent to treat analysis.

3.3. Sample size

The trial's sample size calculation was based on the primary outcome, 6-month BSCVA. We informed the calculation with measurements from the first Steroids for Corneal Ulcers Trial (SCUT), among patients enrolled with between 20/60 and 20/400 vision. The SCUT trial measured BSCVA at baseline, 3-months, and 12-months. We conservatively used the 12-month outcome measure for the calculations since there was no 6-month measurement. The standard deviation of BSCVA at 12 months was 0.293. Since the primary analysis will adjust for baseline BSCVA, we used an estimate of the residual standard deviation, which is $SD_r = SD\sqrt{1 - r^2}$, where r is the correlation between the baseline measure and primary endpoint. In SCUT, the correlation between baseline and 12-month BSCVA among patients with between 20/60 and 20/400 vision at enrollment was 0.216. We thus assumed a residual standard deviation of $0.293\sqrt{1 - 0.216^2} = 0.286$.

Assuming a significance level of 0.05, allowing for approximately 15% loss to follow up, we estimate that we will have 90% power to detect a 1.1-line difference (logMAR 0.11) between groups with 165 study participants per arm (330 total). For the same sample size and under the same assumptions, the detectable difference at 80% power is 1.0-lines (logMAR 0.10). These calculations were based on the standard power formula for the T-test (using an estimated residual standard deviation).

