**The best treatment strategies for fungal keratitis have not been well characterized.** Topical natamycin, a polyene, is the only antifungal agent approved by the Food and Drug Administration (FDA) for treatment of fungal keratitis. The Mycotic Ulcer Treatment Trials (MUTT) I and II, were two NEI-funded randomized double-masked clinical trials that found topical natamycin to be superior to topical voriconazole and no additional benefit of adjuvant oral voriconazole. Two recent randomized clinical trials also failed to demonstrate a benefit of adjuvant intrastromal voriconazole or adjuvant UVX in the treatment of fungal keratitis. However, natamycin is fungistatic and has limited penetration into the corneal layers. Furthermore, outcomes of fungal keratitis with topical natamycin are extremely poor as demonstrated in MUTT II where approximately 50% of patients had full thickness corneal perforation or required TPK despite topical natamycin, topical voriconazole, and adjuvant oral voriconazole.

**Although much less common, acanthamoeba keratitis (AK) may have the most prolonged and severe course of any corneal infection.** AK is typically related to contact lens use and the incidence of these infections varies from as low as 1% to 4-8% of culture positive microbial keratitis cases in countries where contact lens use is common. Topical biguanides such as chlorhexidine 0.02% and Polyhexamethylene biguanide (PHMB) 0.02% are thought to be the most effective available medical therapy. However, large series suggest that only 60% of patients achieve complete cure with medical therapy alone by one year and that almost 50% end up with a poor outcome, defined as requiring TPK or having visual acuity less than 20/80. Furthermore, these medications are highly toxic and cause permanent damage to delicate ocular structures such as limbal stem cells and trabecular meshwork.

**Even if infectious organisms are eliminated, poor vision can result from corneal opacity and irregular astigmatism.** The use of adjuvant corticosteroids has long been debated in the treatment of bacterial

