#### REAGIR:

- Presence of smear or culture positive fungal or acanthamoeba ulcer; smear or culture negative ulcer; or any atypical bacteria (such as *Nocardia*)
- Moderate to severe vision loss, defined as Snellen visual acuity of 20/40 (6/12) or worse
- Corneal thickness  $\geq 350 \mu\text{m}$ , as measured on AS-OCT
- Age over 18 years
- Basic understanding of the study as determined by the physician
- Commitment to return for follow up visits

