## 9.2 SAMPLE SIZE DETERMINATION

**Sample Size Calculation for SCUT II Primary Analysis: BSCVA.** We power the study for each pairwise comparison. Specifically, we will be comparing (Specific Aim 1) CXL plus early steroids (arm 3) versus steroids and sham cross linking (arm 2), and (Specific Aim 2) early steroids with sham CXL (arm 2) versus standard therapy (arm 1). The power calculation was based on the primary outcome, 6-month BSCVA. We informed the calculation with measurements from the first Steroids for Corneal Ulcers Trial (SCUT), among patients enrolled with between 20/60 and 20/400 vision. The SCUT trial measured BSCVA at baseline, 3-months, and 12-months. We conservatively used the 12-month outcome measure for the calculations since there was no 6-month measurement. The standard deviation of BSCVA at 12 months was 0.293. Since the primary analysis will adjust for baseline BSCVA, we used an estimate of the residual standard deviation, which is  $SD_r = SD\sqrt{1 - r^2}$ , where  $r$  is the correlation between the baseline measure and primary endpoint. In SCUT, the correlation between baseline and 12-month BSCVA among patients with between 20/60 and 20/400 vision at enrollment was 0.216. We thus assumed a residual standard deviation of  $0.293\sqrt{1 - 0.216^2} = 0.286$ . Assuming a significance level of  $0.05/2=0.025$ , and allowing for approximately 15% loss to follow up, we estimate that we will have 80% power to detect a 1.4-line difference (logMAR 0.14) between groups with 93 study participants per arm (279 total). This calculation applies to each of the two prespecified primary outcomes for this trial (corresponding to the two separate research questions), and is based on the standard power formula for the T-test (using an estimated residual standard deviation). Note that if the trial were to enroll 60 patients per arm, the minimum detectable effect under all the same assumptions would be 1.8 lines (logMAR 0.18). See SCUT II SAP Section 1.5.6 for details on interim power analysis.

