**SCUT II Effects Stratified by Presence of Drug resistant Organisms.** This analysis is similar to the microbiological outcome in the secondary analyses, in that we contrast culture-positive patients from Arm 3 to culture-positive patients from Groups 1 and 2 (Specific Aim 3). Prior studies suggest a drug resistance to moxifloxacin probability of between 0.34 and 0.43, depending on prior exposure to moxifloxacin. We hypothesize that when drug resistant organisms are present, outcomes will be more favorable when cross-linking is conducted. The outcome variable is visual acuity. We anticipate approximately 80% power to detect a difference of approximately 3 lines in outcomes, assuming 35% of individuals are drug resistant at baseline (based on simulation; details available upon request). The calculation assumed 15% loss to follow-up. This is a prespecified secondary analysis.

See [Section 9.4.1](#) for details regarding pre-specified analyses.

**REAGIR Primary outcome, BSCVA at 6 months.** The sample size calculation for REAGIR used the same assumptions as the SCUT II sample size calculation for BSCVA. Assuming a significance level of 0.05, allowing for approximately 15% loss to follow up, we estimate that we will have 90% power to detect a 1.1-line difference (logMAR 0.11) between groups with 165 study participants per arm (330 total). For the same sample size and under the same assumptions, the detectable difference at 80% power is 1.0-lines (logMAR 0.10). These calculations were based on the standard power formula for the T-test (using an estimated residual standard deviation).

**REAGIR II Primary outcome, BSCVA at 6 months.** The sample size calculation for REAGIR II uses the same assumptions as the SCUT II sample size calculation for BSCVA. Assuming a significance level of 0.05, allowing for approximately 15% loss to follow up, we estimate that we will have 80% power to detect a 5.3-lines difference (logMAR 0.53) between groups with 30 study participants per arm (60 total). For the same sample size and under the same assumptions, the detectable difference at 90% power is 6.1-lines (logMAR 0.61). These calculations were based on the standard power formula for the T-test (using an estimated residual standard deviation).

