6.2. Analysis methods

Primary Outcome

Visual Acuity at 6 months. We will use a multiple linear regression model to estimate the mean difference between groups in BSCVA measured in logMAR at 6 months. The model will include covariates for treatment arm (a binary indicator variable for RB-PDT), indicators for study site (randomization strata), and baseline pinhole visual acuity. We propose a two-sided alpha of 0.05 for the primary analysis.

For study participants who experience perforation or the need for TPK this will be noted and BSCVA will be recorded prior to performing surgery (either corneal glue or TPK). These study participants actual 6-month visual acuity will be used in the primary analysis. As a sensitivity analysis, the last observation (at 3 weeks or 3 months) will be carried forward (LOCF) as the 6-month BSCVA.

The measurement window for the 6-month primary BSCVA outcome will be 5-9 months. The window was chosen after examining the distribution of measurement timing in masked data. As a sensitivity analysis, we will include all participants, including those who had their primary outcome measured out-of-window.

A supplementary analysis using linear mixed effects regression will be conducted to analyze all BSCVA data (including 3-week and 3-month observations). The model will include baseline BSCVA and treatment assignment as covariates (fixed effects) plus a random effect for patient to allow for repeated measures over time. Such analyses will be sharply distinguished from the primary pre-specified analysis. Permutation testing will be the basis of inference. Specifically, we will conduct 10,000 random permutations of treatment assignment, and conduct the primary regression analysis on these re-randomized data sets. We will then compare the observed regression coefficients to the randomization distribution, reporting the quantiles.

In all analyses, model adequacy will be checked by examination of residuals or other goodness of fit tests as needed. Inadequate model fit will prompt us to report alternative models. If there are chance imbalances in prognostic baseline patient characteristics, a secondary analysis will include them as covariates in the regression model.

Secondary Outcomes

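### REAGIR's stated 90% power for 0.11 logMAR rests on a residual SD taken from bacterial SCUT eyes in a limited acuity band, and the documents do not support applying it to REAGIR's population

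*SAP*

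**What the plan says.** SAP 3.3 takes an SD of 0.293 for 12-month BSCVA and a baseline correlation of 0.216 from the first SCUT trial, and derives a residual SD of 0.286. On the source of these inputs it says: "We informed the calculation with measurements from the first Steroids for Corneal Ulcers Trial (SCUT), among patients enrolled with between 20/60 and 20/400 vision". Its power statement reads: "we estimate that we will have 90% power to detect a 1.1-line difference (logMAR 0.11) between groups with 165 study participants per arm". It adds, for the same sample size: "the detectable difference at 80% power is 1.0-lines (logMAR 0.10" in logMAR units. Both allow about 15% loss. SAP 6.2 sets the test level: "We propose a two-sided alpha of 0.05 for the primary analysis".

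Protocol 9.2 carries the inputs across from the bacterial trial: "The sample size calculation for REAGIR used the same assumptions as the SCUT II sample size calculation for BSCVA". The SCUT II paragraph there gives the same source band: "among patients enrolled with between 20/60 and 20/400 vision". Protocol 2.2 describes SCUT as a trial of culture-positive bacterial ulcers.

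For REAGIR, Protocol 5.1 admits fungal, acanthamoeba, smear- or culture-negative and atypical bacterial ulcers. Its acuity criterion is: "Moderate to severe vision loss, defined as Snellen visual acuity of 20/40 (6/12) or worse". There is no lower limit for the study eye; the only acuity exclusion in Protocol 5.2 concerns the unaffected eye.

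**The concern.** The planning SD comes from a population that differs from REAGIR's in two ways. The organism differs: SCUT was bacterial and REAGIR is mainly non-bacterial. The acuity range differs too: SCUT eyes between 20/60 and 20/400 (logMAR 0.48 to 1.30) stand in for eyes at 20/40 (logMAR 0.30) or worse with no floor.

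Protocol 2.2 gives reason to expect more variable outcomes. About half the patients in one cited fungal trial perforated or needed a therapeutic graft. Of acanthamoeba patients it says "almost 50% end up with a poor outcome, defined as requiring TPK or having visual acuity less than 20/80". A population split near half between good and poor results could well have a larger SD than the bacterial band did.

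The only conservatism the plan claims is the use of a 12-month outcome in place of a 6-month one. That addresses neither difference. The supplied text gives no SD range and no re-estimation step. At stake is how a null or inconclusive result would be read against a claim of 90% power for about one line. The SD that feeds the futility calculation in SAP 3.5 is also affected.

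**Working it through.** **Inputs.** SD 0.293, r 0.216, 165 per arm, 15% loss (SAP 3.3); two-sided alpha 0.05 (SAP 6.2). REAGIR II: 30 per arm, 15% loss, alpha 0.05, detectable differences 0.53 (80% power) and 0.61 (90%) (Protocol 9.2).

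**Step 1: reproduce the plan.**
- Residual SD = 0.293 × √(1 − 0.216²) = 0.286.
- Evaluable per arm = 165 × 0.85 = 140.25, taken as 140.
- Power comes from the two-sample t-test with noncentrality δ / (SD × √(2/n)). For δ = 0.11, this is 0.11 / (0.286 × √(2/140)) = 3.22, giving 89.4% power (stated: 90%).
- The detectable difference is 0.111 at 90% power and 0.096 at 80% (stated: 0.11 and 0.10).

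The arithmetic is sound, so the question is only about the SD.

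**Step 2: vary the SD.** The documents give no SD for the eligible population, so every row after the first is an assumption. All rows use 140 evaluable per arm.

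| Residual SD | Power for 0.11 | Difference detectable at 90% power |
|---|---|---|
| 0.286 (plan) | 89% | 0.111 |
| 0.327 | 80% | 0.127 |
| 0.40 | 63% | 0.156 |
| 0.50 | 45% | 0.194 |

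Power falls to 80% at an SD only 14% above the plan's (0.327 / 0.286 = 1.14).

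**Step 3: check Protocol 9.2 against itself.** REAGIR II is said to use the same assumptions.
- Evaluable per arm = 30 × 0.85 = 25.5.
- At SD 0.286 the detectable differences are 0.229 (80%) and 0.265 (90%), not 0.53 and 0.61.
- For fixed n the detectable difference is proportional to the SD. The implied SD is therefore 0.286 × 0.53 / 0.229 = 0.66 from the first figure and 0.286 × 0.61 / 0.265 = 0.66 from the second.

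Both REAGIR II figures agree with each other at about 0.66 and disagree with the stated input of 0.286.

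**Step 4: the futility rule.** SAP 3.5 bases conditional power on the original alternative hypothesis and names no SD. As an illustration, assume 50 per arm observed with a difference of 0.02, 90 per arm still to come, and a future effect of 0.10. The table compares conditional power with future patients simulated at 0.286 or at the assumed true SD.

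| Assumed true SD | Future at 0.286 | Future at true SD |
|---|---|---|
| 0.40 | 41% | 28% |
| 0.47 | 31% | 19% |
| 0.50 | 27% | 17% |

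In this example the choice crosses the 20% threshold only once the true SD is about 0.47 or more.

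**The case against.** The strongest reply is that a different population does not prove a larger residual SD, and several parts of that reply stand.

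- **Acuity band.** If outcome is linear in baseline acuity with constant scatter, restricting the baseline range lowers the correlation but leaves the residual SD unchanged. The low r of 0.216 (under 5% of variance) may itself reflect the restriction. So the band alone does not show that 0.286 is too small; the case rests on outcomes being more variable in non-bacterial and very poor eyes.
- **Background rates.** Protocol 2.2 reports event and poor-outcome rates, not acuity SDs. REAGIR excludes impending perforation and descemetocele and requires at least 350 µm of cornea, so those rates need not transfer.
- **SCUT II.** A reader might infer that SCUT II is also underpowered. It enrols bacterial ulcers, as SCUT did, and only the acuity range differs. The documents show no shortfall there.
- **Perforated and grafted eyes.** A reader might infer that SAP version 7, by using their actual 6-month acuity, widens the spread further. The values it replaced were carried forward from eyes that perforated or needed a graft and may also be extreme. The documents give no direction.
- **Futility.** A reader might infer that the conditional power will be wrong. SAP 3.5 does not say which SD is used, and the guidance is advisory.
- **Inference.** The primary test and its 95% interval use the observed variance. Neither type I error nor the estimate depends on 0.286.

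None of this supplies a reason for applying the bacterial SD to REAGIR's organisms, and none of it explains the REAGIR II figures.

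**Conclusion.** The point holds for REAGIR as a lack of support for the planning SD. The claims of 90% power for 0.11 and 80% for 0.10 are correct only if the residual SD is about 0.286, and that value comes from eyes with a different class of infection and a different acuity range. The documents do not show the true SD. It would therefore be wrong to conclude that REAGIR's power is 63%, 45% or any other particular figure; those are scenarios that show how quickly the claim erodes.

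The REAGIR II conflict rests on no assumption beyond the protocol's own inputs. It shows that the planning figures within Protocol 9.2 disagree by more than a factor of two in SD (0.66 against 0.286). It does not show which SD is right.

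**What to change.** 1. Keep 0.286 and its source on record in SAP 3.3 and Protocol 9.2 as the basis on which N was chosen.
2. Add to both sections the residual SD of 6-month BSCVA estimated from pooled, masked REAGIR data, using the primary model's baseline acuity and site terms without treatment arm. Pooling over arms adds little: for a true difference of 0.11 the extra variance is 0.11² / 4 = 0.003, which would move 0.286 to √(0.0818 + 0.0030) = 0.291.
3. Restate power and detectable difference from that SD, with a range around it.
4. State in SAP 3.5 that the conditional-power simulation uses that SD together with the original one-line effect.
5. Reconcile the REAGIR II detectable differences with the stated assumptions, or state the different SD behind them.
6. For SCUT II, a sensitivity range for the SD is enough.

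Do not change N. The cost is one masked variance estimate and short edits to three sections. SAP 6.2 records that masked data were already examined to set the outcome window, so the step has a precedent in this trial. The drawback is that the stated detectable difference may become less favourable.

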3.4. Statistical framework

The trial will use a superiority test of the hypothesis that patients who receive the RB-PDT adjuvant will have better BSCVA outcomes compared with patients who receive sham RB-PDT. The analysis will be intention-to-treat (ITT), with all patients analyzed according to their randomized allocation.

3.5. Statistical interim analyses and stopping guidance

The Data and Safety Monitoring Committee will meet to review the interim efficacy data when primary outcome data is available on 100 study subjects (approximately 1/3 of the 330 target enrollment).

The DSMC will make one of the following recommendations:

- Continue the trial without modifications
- Continue the trial with study modifications
- Terminate enrollment or treatment in the trial because of efficacy
- Terminate enrollment or treatment in the trial because of futility
- Terminate enrollment or treatment in the trial because of safety concerns

The DSMC will determine the database closure dates for each report in advance; archival copies of the (a) main SQL database, and (b) study analysis file as they exist at the time of each report will be maintained. All reports will be sent using secure email to the members of the DSMC two weeks prior to each meeting.

The DSMC will make decisions with the benefit of pre-specified decision guidelines. These guidelines were agreed upon at the initial meeting, and take into consideration (a) safety, (b) efficacy, (c) clinical importance, and (d) validity.

Efficacy. An unmasked interim analysis will be conducted when 100 participants (approximately 1/3) reach the primary endpoint to determine whether or not sufficient evidence has accumulated to justify stopping the trial because one treatment is clearly superior (and therefore should be extended to all future cases). The guidelines for efficacy will use group sequential boundaries for judging the statistical significance of the primary outcome measure. We propose to use a Lan-DeMets flexible alpha spending approach, with $\alpha^*(t^*) = \alpha (t^*)^\theta$, where $\theta = 3.02$ (chosen so that the two-sided P -value to stop the trial for efficacy is 0.0005) [1]. The interim analysis for efficacy as well as for futility will be conducted with equal weight for each of the two contrasts. This boundary corresponds to an effect size of 1.8 lines (0.18 logMAR).

Futility. Early discontinuation due to the unlikelihood of significant findings conditional on interim results may be considered, based on the original sample size considerations. For evaluating futility, we propose discontinuation for futility if the conditional power to detect a one line *benefit* drops below 20% at the interim analysis [2]. Conditional power will be derived by simulation of the unobserved future patients according to the original alternative hypothesis. Our proposed futility guidance is one-sided, and is subordinate to efficacy analyses.

Harm. Stopping for harm will be done at the judgment of the DSMC. Several endpoints will be examined, including (a) the best spectacle-corrected visual acuity at six months, (b) adverse events, and especially (c) serious adverse events, including corneal perforation or mortality. While the analysis would consider unbalanced distribution of predictive factors such as (a) infiltrate/scar size at presentation, (b) organism, and (c) repeat culture status, it is recognized that ethical considerations require careful considerations of statistical tests as well as qualitative judgments in the light of experience.

All subjects who provide informed consent will be accounted for in this study. We will present the number lost to follow-up and the number of protocol deviations by arm. The proportion of

subjects reporting adverse events and serious adverse events will be reported by arm to the DSMC and will be compared using a Fisher's Exact Test.

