4.1. Confidence intervals and *P*-values

We will test for difference between arms in the primary outcome (BSCVA at 6 months follow-up) using a $p=0.05$ level to assess statistical significance. We will construct two-sided 95% confidence intervals to test for superiority of RB-PDT versus sham.

We will report 95% confidence intervals on our measures of effect (difference in BSCVA logMAR) on each secondary outcome. We do not plan to adjust secondary outcome confidence intervals for multiplicity because we expect them to be highly correlated and together they provide corroborating evidence for or against the primary outcome hypothesis.[3]

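### REAGIR's interim efficacy boundary contradicts itself: theta = 3.02 at alpha 0.05 gives a stopping P of about 0.0014 to 0.0018, not the stated 0.0005, and the final test still uses the full 0.05

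*SAP*

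**What the plan says.** SAP Section 3.5 plans one unmasked efficacy look, timed "when primary outcome data is available on 100 study subjects (approximately 1/3 of the 330 target enrollment"). For the boundary, it states: "We propose to use a Lan-DeMets flexible alpha spending approach", of the form alpha × t^theta. The exponent theta is 3.02, "chosen so that the two-sided P -value to stop the trial for efficacy is 0.0005". The paragraph goes on: "The interim analysis for efficacy as well as for futility will be conducted with equal weight for each of the two contrasts". It ends: "This boundary corresponds to an effect size of 1.8 lines (0.18 logMAR").

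The trial-level alpha is in two other places. Section 6.2 says: "We propose a two-sided alpha of 0.05 for the primary analysis". Section 4.1 tests the primary outcome "using a $p=0.05$ level to assess statistical significance", with two-sided 95% confidence intervals. Neither section gives a final level reduced for the interim look.

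**The concern.** Section 3.5 describes a single boundary in three ways: by the spending exponent, by a nominal P-value and by an effect size. At a first look, the nominal two-sided P equals the alpha spent, so any one of these, together with the information fraction, SD and sample size, fixes the other two. The three figures given do not agree.

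The boundary governs an unmasked recommendation to terminate for efficacy. If it has two values, it has not been pre-specified, and the alpha spent at the look cannot be reported without ambiguity.

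Two further points sit beside this. REAGIR has two arms and one primary contrast, so weighting two contrasts has no meaning here and could be taken as an instruction to split alpha. In addition, a Lan-DeMets design that spends part of 0.05 at the interim does not leave the full 0.05 for the final test.

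**Working it through.** **Inputs**
- Two-sided alpha 0.05 (SAP 4.1 and 6.2; Protocol 9.2 for REAGIR).
- Spending function alpha × t^3.02, interim at 100 of 330 (SAP 3.5).
- Residual SD 0.293 × √(1 − 0.216²) = 0.286; 165 per arm; 15% loss (SAP 3.3).
- 1:1 allocation (SAP 3.1), so about 50 per arm at the interim.

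**Check on the shared inputs.** With 165 × 0.85 = 140.25 per arm and SD 0.286, power for 0.11 logMAR is 89.6% (the SAP states 90%). The detectable difference at 80% power is 0.096 (the SAP states 0.10). The SD and sample size therefore reproduce the SAP's own design figures, and the mismatch lies in the boundary paragraph.

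**From theta to P and effect.** SE at the interim = 0.286 × √(2/50) = 0.0572. Boundary effect = z × SE.

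| Information fraction t | P = 0.05 × t^3.02 | P / 0.0005 | z | Effect (logMAR) |
|---|---|---|---|---|
| 100/330 = 0.303 | 0.00136 | 2.7 | 3.203 | 0.183 |
| 1/3 | 0.00181 | 3.6 | 3.119 | 0.178 |
| 100/280.5 = 0.357 (expected completers) | 0.00222 | 4.4 | 3.059 | 0.175 |

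**From the stated P to effect and theta.** P = 0.0005 gives z = 3.481 and an effect of 3.481 × 0.0572 = 0.199 logMAR, or 2.0 lines. The theta required is ln(0.0005/0.05)/ln(t), which is 3.86 at t = 100/330 and 4.19 at t = 1/3.

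**From the stated effect to P.** 0.18/0.0572 = 3.147, so the two-sided P is 0.00165. With the unadjusted SD of 0.293, P is 0.0021.

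**Attempts to recover 0.0005**
- Halving alpha to 0.025 for two contrasts gives 0.00068 (t = 100/330) to 0.00091 (t = 1/3).
- Alpha 0.0125 gives 0.00034, 0.00045 and 0.00055 at the three fractions in the table. This is the only variant near 0.0005. REAGIR uses that alpha nowhere, and it would put the boundary at about 2.0 lines, not 1.8.
- Assuming 55 per arm, P = 0.0005 still needs 0.190 logMAR.

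Alpha 0.0125 is the per-side half of 0.025, which is SCUT II's per-comparison level (Protocol 9.2 and 9.4.1). Together with the two-contrasts wording, this suggests text carried over from SCUT II. That is an inference, because the SCUT II SAP is not among the documents.

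**Probability of crossing, Φ(δ/SE − z)**

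| True difference | P = 0.0005 | theta = 3.02, t = 100/330 | theta = 3.02, t = 1/3 |
|---|---|---|---|
| 0.18 logMAR | 37% | 48% | 51% |
| 0.11 logMAR (design effect) | 6.0% | 10.0% | 11.6% |

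**Final test.** The interim and final statistics are taken as bivariate normal with correlation √t.

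| Interim boundary | Overall two-sided error, final test at 0.05 | Final nominal level that holds 0.05 |
|---|---|---|
| theta = 3.02, t = 100/330 | 0.0507 | 0.0493 |
| theta = 3.02, t = 1/3 | 0.0509 | 0.0491 |
| theta = 3.02, t = 100/280.5 | 0.0511 | 0.0489 |
| P = 0.0005, any of these t | 0.0502 | 0.0498 |

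**The case against.** The strongest reply concerns how much this matters, since no reading tried makes the three figures agree.

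- **The P-value may be the intended anchor.** Section 3.5 presents 0.0005 as the target and theta as derived from it, so a committee might simply apply 0.0005, the stricter value. That is plausible, but the 1.8-line figure in the same paragraph then contradicts the rule being applied.
- **The boundary is guidance.** It is weighed with safety, clinical importance and validity. This is true, but Section 3.5 also says the guidelines are pre-specified and use group sequential boundaries. Discretion does not settle which boundary was specified.
- **The practical gap is modest at the design effect.** At 1.1 lines the two readings differ in about 4 to 6% of trials (10.0 − 6.0 and 11.6 − 6.0), and under the null in about 0.1% (0.00136 − 0.0005 and 0.00181 − 0.0005). This stands. The larger gap at 1.8 lines assumes a true effect about 1.6 times the design effect.
- **The final-level point is small.** This stands. Section 6.2 alone could be read as naming the overall alpha, but Section 4.1's 0.05 level and 95% interval point to an unadjusted final test.
- **The normal approximation matters slightly.** With t on 98 degrees of freedom, the theta = 3.02 boundary is 0.189 at 100/330 and 0.183 at 1/3, while P = 0.0005 needs 0.206. The match to 1.8 lines is then looser, and the conflict with 0.0005 remains.
- **The information fraction is not defined.** This stands, and the repair has to settle it.

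**Conclusion.** The concern holds. With alpha 0.05, theta = 3.02 implies a stopping P of 0.0014 to 0.0018 on the SAP's own fractions (0.0022 against expected completers). That agrees with a boundary of about 1.8 lines. The stated 0.0005 is too small by a factor of 2.7 to 3.6 and would need about 2.0 lines. Interim differences between roughly 1.8 and 2.0 lines therefore lead to opposite recommendations depending on which figure is used.

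The reference to two contrasts is wrong for a two-arm trial, whatever its source. Using the full 0.05 at the end departs from the spending design that the SAP adopts, but it adds at most about 0.001 to the type I error.

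The effect sizes rest on SD 0.286, 50 per arm and a normal approximation. The P-values implied by theta rest only on alpha and t. The point must be fixed because it leaves a termination rule with two values, although the expected numerical effect on the trial's error rates is small.

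**What to change.** Amend SAP Section 3.5 as follows.

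1. Define the information fraction first: say whether the denominator is the 330 enrolled or the expected number with primary outcome data.
2. State one set of figures that agree. At t = 100/330 the choices are:
   - (a) theta = 3.02, alpha 0.05, nominal P 0.0014, about 1.8 lines; or
   - (b) nominal P 0.0005, theta 3.86, about 2.0 lines.

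   If the denominator is expected completers (t = 100/280.5), (a) becomes P = 0.0022 with a boundary of 0.175 logMAR. For (b), theta becomes about 4.46, because theta = 3.86 would then spend about 0.0009.
3. Delete the sentence on two contrasts.
4. In Sections 4.1 and 6.2, take the final nominal level and the matching confidence level from the spending function: about 0.0493 for (a) and 0.0498 for (b) at t = 100/330.
5. If the interim look has already taken place, record in the revision history which boundary was applied and the alpha spent, and derive the final level from that.

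The cost is SAP wording only. The sample size does not change, and the final critical value moves from 1.960 to about 1.966 under (a) or 1.962 under (b).
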